7.1.3.2. Modified Intention-To-Treat (ITT) Population

All enrolled subjects except subjects who meet the anti-hypertensive medication escape criteria (OSBP \geq 180 mmHg or safety reasons) will be excluded from the modified intention-to-treat population. Office and ambulatory blood pressure outcomes from procedure up to 3 months will be presented for this population.

7.1.3.3. Per Protocol Population

All treated subjects, meeting the following criteria:

1. Subjects showing medication compliance in blood and/or urine (via drug testing data) at screening visit 2 (SV2) and 3-months.
2. Exclude subjects with protocol deviation code 101 (consent not obtained).
3. Exclude subjects who do not meet the following Inclusion/Exclusion criteria.
 - Inclusion: Individual has an office systolic blood pressure (SBP) \geq 150 mmHg and $<$ 180 mmHg and an office DBP \geq 90 mmHg measured at SV2, according to the guidelines in Appendix 16.5 of the study protocol.
 - Inclusion: Individual has a 24-hour ABPM average SBP \geq 140 and $<$ 170 mmHg measured at SV2, according to guidelines in Appendix 16.5 of the study protocol.
 - Exclusion: Individual has undergone prior renal denervation.
 - Exclusion: Individual has renal artery anatomy that is ineligible for treatment.
 - Exclusion: Individual has one or more of the following conditions: stable or unstable angina within 3 months of enrollment, myocardial infarction within 3 months of enrollment; heart failure; cerebrovascular accident or transient ischemic attack or atrial fibrillation at any time.
4. Exclude Subjects meeting the anti hypertensive medication escape criteria (OSBP \geq 180 mmHg or safety reasons).
5. Exclude subjects who did not receive the treatment.

Office and ambulatory blood pressure outcomes up to 3 months will be presented for this population.

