### **9.1.4. Screening Visit 2**

Screening Visit 2 must occur within three to four weeks of completion of SV1. The following assessments will be performed at Screening Visit 2:

- a) **Clinical assessment** will be conducted to further evaluate for prior or existing medical conditions that would exclude subjects from participation in the study and to establish the subject's baseline medical condition. An individual experienced in performing histories and

physical exams is required to assess subjects for safety assessment during the period of time that study subjects are not on antihypertensive medications.

- b) **Office blood pressure measurements** will be obtained in accordance with **Appendix 16.5**. The average office blood pressure value will be used as the baseline value for comparison with follow-up visit office blood pressure values. Subjects with an office systolic blood pressure  $\geq 150$  and  $< 180$  mmHg and an office DBP  $\geq 90$  mmHg are eligible to continue the screening process.
- c) **Laboratory tests:**
  - **Basic metabolic panel Chem-7 (blood):** serum-creatinine, sodium, potassium, blood urea nitrogen (BUN) or urea, bicarbonate, chloride, and glucose. Bicarbonate will not be measured for subjects enrolled in Europe.
  - **eGFR** will be calculated from the serum-creatinine in the Chem-7 panel for eligibility criteria by using the 4 variable Modification of Diet in Renal Disease (MDRD) Formula **Note:** If eGFR  $\geq 42$  and  $< 45$  mL/min/1.73m^2 then subject can be retested after hydration with a single, repeat test within two weeks.
  - **hCG pregnancy test in blood/urine** for female subjects who are not postmenopausal. (This may also be completed the day of the procedure).
  - **Drug testing (urine/blood)** to ensure medications are no longer present in the subject's system. A urine sample will be collected, preferably using the subject's first morning urine. A blood sample will be collected at the time of the visit. Drug testing samples collected for subjects that screen fail after obtaining the sample, must not be sent to the core lab for analysis.

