- **Renal artery imaging** will be performed at the 6-month follow-up visit to assess if a renal artery stenosis is suspected. A renal duplex ultrasound (DUS) will be obtained at 6-months follow up and submitted to the DUS Core Laboratory. If the DUS is determined to be nondiagnostic a repeat DUS, a MRA, CT or angiogram will be performed (repeat imaging is to be completed within 30 days after confirmation of non-diagnostic imaging). If evidence of a clinically significant stenosis is indicated by the DUS or MRA/CT Core Laboratory, an angiogram must be obtained and submitted to the angiographic core laboratory.
  - If renal imaging is not obtained at the 6-month follow-up visit due to extenuating circumstances, renal imaging is required at the next scheduled study visit.
- **24-hour ABPM** will be conducted at the 3, 6, and 12-month follow-up visits post-procedure according to the guidelines in **Appendix 16.5**. A repeat ABPM will be required in the event of technical issues, failure to follow ABPM guidelines or if the minimum required number of daytime and nighttime readings is not obtained. If ABPM is repeated office blood pressure and drug testing (for 3-month follow up only) must be repeated on day the ABPM is applied.
  - Initiate medication re-Introduction for subjects with systolic OBP  $\geq 140$  mmHg at 3-month follow-up visit. Starting at the 3-month follow up after clinical assessment and a valid ABPM are completed.
- **Mortality assessment** will be completed by the investigational site when a subject cannot be reached after each of the protocol required follow-up visits.
- **Drug testing** (urine/blood) to ensure medications are no longer present in the subject's system. A urine sample will be collected, preferably using the subject's first morning urine. A blood sample will be collected at the time of the visit. Drug testing samples collected for subjects that screen fail after obtaining the sample, must not be sent to the core lab for analysis.

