#### 13.2.3. *Per Protocol Population*

All treated subjects, meeting the following criteria are included in the per protocol population analysis::

1. Subjects showing medication compliance in blood and/or urine (via drug testing data) at Screening Visit 2 (SV2) and three months post-procedure.
2. Exclude subjects with protocol deviation code 101 (consent not obtained).

3. Exclude subjects who do not meet the following inclusion/exclusion criteria:

- Inclusion: Individual has an office systolic blood pressure (SBP)  $\geq 150$  mmHg and  $< 180$  mmHg and an office DBP  $\geq 90$  mmHg measured at Screening Visit 2, according to the guidelines in **Appendix 16.5** of the CIP.
- Inclusion: Individual has a 24-hour ABPM average SBP  $\geq 140$  and  $< 170$  mmHg measured at Screening Visit 2, according to guidelines in **Appendix 16.5** of the study protocol.
- Exclusion: Individual has undergone prior renal denervation.
- Exclusion: Individual has renal artery anatomy that is ineligible for treatment.
- Exclusion: Individual has one or more of the following conditions: stable or unstable angina within three months of enrollment, myocardial infarction within three months of enrollment; heart failure, cerebrovascular accident or transient ischemic attack, or atrial fibrillation at any time.

4. Exclude subjects meeting the anti-hypertensive medication escape criteria (OSBP  $> 180$  mmHg or safety reasons).

Office and ambulatory blood pressure outcomes out to three months will be presented for this population.

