11.6. Appendix VI: Selection of Drug Testing Values at Follow-Up

The analysis windows are defined as follows:

Study Visit	Target Date (post procedure)	Protocol Defined Window (post procedure)	Expanded Analysis Window (post procedure)
3 Months	90	76-104	46-135

Scenario 1: There are multiple ABPM raw data records with the same ABPM CPEVENT including SV2:

1. Starting with the most recent ABPM raw record, is there any Drug Testing visit (SCHEDULED or UNSCHEDULED) where 'Drug testing sample performed date' = 'ABPM start date'?
2. If yes, then use that Lab visit if it is in the expanded analysis window.
3. If no, then go to the previous ABPM raw record, and again look for any Lab visit (SCHEDULED or UNSCHEDULED) where 'Drug testing sample performed date' = 'ABPM start date'. If yes, then use that drug testing visit if it is in the expanded analysis window. In no, then go to the previous ABPM raw record...
4. Repeat for all ABPM raw records.

Scenario 2: There is only 1 ABPM raw data record for a given CPEVENT:

This algorithm only applies to the follow up measurements in the tables above. Drug testing sample performed date will be used as drug testing follow up date. In case of multiple SV2 measurements, then take the latest one.

1. Time to follow up will be calculated as (Drug testing sample performed date – procedure date). Only SCHEDULED follow up data will be included in this analysis; If there are multiple measurements per subject per site reported visit (CPEVENT), the most recent one will be taken before applying the expanded analysis window algorithm below.
2. All follow up measurements <46 days post procedure will not be included in the follow up analysis unless otherwise specified.
3. The remaining measurements will be categorized per windows defined above. In case of multiple qualifying measurements, first take the one closest to the target follow up date, then take the latest one.

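### Per-protocol drug-test compliance is undefined when blood and urine disagree, and SAP Appendix VI cannot select a repeated SV2 drug test

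*SAP*

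**What the plan says.** Criterion 1 of the per-protocol set in SAP 7.1.3.3 keeps "Subjects showing medication compliance in blood and/or urine (via drug testing data) at screening visit 2 (SV2) and 3-months". Protocol 13.2.3 has the same rule: "Subjects showing medication compliance in blood and/or urine (via drug testing data) at Screening Visit 2 (SV2) and three months post-procedure". Neither document defines compliance or mentions discordant results.

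Both matrices are planned at both visits. Protocol 9.1.4 says of SV2 "A urine sample will be collected, preferably using the subject's first morning urine", with a blood sample as well. Protocol 9.1.6 repeats the urine text for follow-up and adds "A blood sample will be collected at the time of the visit". The purpose given in 9.1.4 is "to ensure medications are no longer present in the subject's system".

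SAP Appendix VI selects which drug-test sample is used. Its Scenario 1 applies when "There are multiple ABPM raw data records with the same ABPM CPEVENT including SV2". The selected sample is subject to this condition: "If yes, then use that Lab visit if it is in the expanded analysis window". The appendix table has one row, 3 months, with an expanded window of day 46 to 135 post-procedure. Protocol 9.1.4 requires a repeat drug test on the day a repeat SV2 ABPM is applied.

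SAP 7.7.2.1 makes ITT the primary population and per protocol a secondary one.

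**The concern.** The study compares two cohorts that are both meant to be off antihypertensive drugs. A drug found in either matrix contradicts that state, but the and/or wording can be satisfied by one clean matrix. A drug present at 3 months would be credited to denervation. A drug present at SV2 would lower the baseline and hide part of the response.

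The comparator is external and not randomised. If the rule stays open, discordant subjects could be classified differently in the two cohorts, or the choice could be made after the results are known.

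The Appendix VI problem runs the other way. Read literally, it leaves a subject with a repeated SV2 ABPM without a usable SV2 drug result. That subject could then not meet criterion 1, even if every sample was clean.

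**Working it through.** The documents state no figure that depends on this rule, so there is nothing to reproduce. The check is one of logic, followed by an illustration of size.

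**1. The criterion at one visit**

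| Blood | Urine | One clean matrix is enough | Every tested matrix must be clean |
|---|---|---|---|
| negative | negative | kept | kept |
| negative | positive | kept | excluded |
| positive | negative | kept | excluded |
| positive | positive | excluded | excluded |

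The readings differ only for discordant subjects. A third reading, that whichever matrix was tested must be clean, matches the last column when both results exist and uses the available result when one is missing. The text allows all of these. The purpose stated in protocol 9.1.4 fits the last column.

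**2. Whether another rule catches a discordant subject**

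- Eligibility (protocol 8.3 and 8.4): no criterion refers to the drug-test result. Inclusion 5 asks only for willingness to discontinue medication.
- ITT and modified ITT (SAP 7.1.3.1 and 7.1.3.2): neither has a drug-test criterion. Modified ITT deals with medication escape only.
- Appendix VI: it selects samples by date and never combines the blood and urine results.

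**3. Appendix VI when the SV2 ABPM was repeated**

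- Two SV2 ABPM records put the subject in Scenario 1, which names SV2.
- The repeat drug test falls on the repeat ABPM's start date, so the date match succeeds.
- The sample must then lie between day 46 and day 135 after the procedure. SV2 precedes the procedure, so its day count is negative and the condition fails.
- Going back to the previous ABPM record fails for the same reason, and the scenario gives no further fallback.
- The instruction to take the latest of several SV2 measurements sits under Scenario 2, which applies only when there is a single ABPM record.

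Appendices II (office BP) and V (laboratory values) also pair SV2 with a post-procedure window in Scenario 1.

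**4. Illustration of size**

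Shift in the DYSTAL mean = m × e / n, where

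- m = discordant subjects who are on drug, assumed 1 to 5
- e = drug effect on 24-h SBP, assumed 5 to 10 mmHg
- n = per-protocol subjects: 50 is the planned treated number (SAP section 6), and 45 is an assumed smaller set

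Smallest: 1 × 5 / 50 = 0.10 mmHg. Largest: 5 × 10 / 45 = 1.11 mmHg (with n = 50, 5 × 10 / 50 = 1.00).

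For scale, SAP section 6 cites a fall of 5.5 mmHg in 38 subjects, 95% CI -9.1 to -2.0. The half-width is (9.1 - 2.0) / 2 = 3.55, and with t = 2.026 on 37 df the standard error is 3.55 / 2.026 = 1.75 mmHg. The top of the range is 1.11 / 1.75 = 0.63 of that standard error.

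A drug present at 3 months exaggerates the fall. The same drug present only at SV2 shrinks it by the same amount.

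**The case against.** The strongest reply is that the plan nowhere says a subject with a drug in one matrix counts as off drug. Compliance is undefined, and and/or may simply mean whichever samples were tested, which the purpose of testing supports. This stands: the defect is an undefined term, and a reader who infers that one negative matrix is the settled rule goes beyond the text. The reply does not remove the gap, because the literal wording also permits the lenient reading and nothing else in either document closes it.

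A reader might also infer that per protocol is the trial's only check on medication use. It is not. Medication is reviewed at each follow-up visit (protocol 9.1.6), and antihypertensive use is summarised at baseline and each follow-up (SAP 7.6). What can be said is that only the per-protocol set applies a drug-test criterion. Nor do the documents say why two matrices are taken, so no argument should rest on each detecting what the other misses.

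On Appendix VI, the reply is that its title refers to follow-up, so a visit without a window has none to fail, and that the line under Scenario 2 shows SV2 results were meant to be used. That is probably the intention. But Scenario 1 names SV2 and attaches the window condition, so the stated algorithm fails there and a programmer would have to guess.

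On size, every input to the shift except the 50 is assumed. The shift is within DYSTAL, and similar contamination in the comparator would partly cancel in the difference. Both remarks stand.

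**Conclusion.** The point holds in a limited form. The per-protocol criterion does not define compliance when blood and urine disagree, and its literal wording permits a subject positive in one matrix to be kept, contrary to the purpose of the testing. Separately, Appendix VI Scenario 1 cannot select an SV2 drug test when the SV2 ABPM was repeated.

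Both drug-test points affect only the secondary per-protocol analysis. It would be wrong to conclude that the primary result is biased by this wording: the ITT analysis uses no drug-test criterion and is the same under every reading, and the study has no powered hypothesis. The documents give no discordance rate, no drug effect and no count of repeated SV2 ABPMs, so the range of about 0.1 to 1.1 mmHg is an illustration and not an estimate. It applies to a simple DYSTAL mean. The effect on the stratified difference would also depend on which strata the subjects fall in and on the comparator's own discordant subjects. Whether discordance differs between the cohorts cannot be judged from the documents.

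**What to change.** Replace criterion 1 in SAP 7.1.3.3 and protocol 13.2.3 with:

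> No antihypertensive drug detected in any matrix tested (blood or urine) at SV2 and at 3 months; if one matrix is missing, classify on the available one and flag it.

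Apply the same rule to the SPYRAL HTN-OFF MED RDN subjects where matrix-level results are available. The documents do not say which matrices that study tested or how results were stored, so the SAP should state what is available and report any difference in classification as a limitation.

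In Appendix VI Scenario 1, limit the window condition to post-procedure visits. For SV2, use the drug test taken on the day of the ABPM used as baseline. Align the same wording in Appendices II and V.

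The cost is a few sentences in the SAP and one in the protocol, with no new samples. The downside is a slightly smaller per-protocol set.

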### ***9.1.9. Anti-hypertensive medication escape criteria***

In the event a subject's office SBP  $\geq$ 180 mmHg, or there is a safety concern, from discharge up to and including the 3-month visit, the subject will be seen a second time within 72 hours for a repeat office BP. If the subject's office SBP remains  $\geq$ 180 mmHg, the subject will be put back on an antihypertensive medication regimen per the investigator's discretion. All efforts should be made to obtain an ABPM and Chem-7 panel, and urine and blood for antihypertensive drug testing, prior to the subject being put back on medications. If the subject already started medications, the subject and investigator should consider if it is safe to take the subject off medications for at least two weeks prior to the 3M visit in order to obtain the requirements at the 3-month visit to ensure endpoint data is collected. The subject will be exited from the off medications portion of the study and will be followed according to **Table 4**. If the subject's office SBP < 180 mmHg, the subject will continue to be followed per **Table 3**. At any time while the subject is not taking antihypertensive medications, either the subject or the investigator may restart antihypertensive medications if there is a safety concern and the subject will be followed according to **Table 4**. All blood pressures must be taken according to the guidelines in **Appendix 16.5** with the exception of needing to be completed by 10:30 am. Visits for monitoring the subject's BP for these purposes must be documented on the CRF.

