7.1.3. Analysis Sets

7.1.3.1. Intention-To-Treat (ITT) Population

All enrolled subjects are included in the intention-to-treat population. Subjects who meet the antihypertensive medication escape criteria (confirmed OSBP \geq 180 mmHg or safety reasons) will be analyzed using Last Observation Carried Forward (LOCF) for their blood pressure measurements, safety outcomes, and office and ambulatory blood pressure outcomes from procedure up to 3 months will be presented for this population.

The LOCF will be determined for the subjects who meets all following criteria:

1. Include any office or ambulatory BP values performed \leq escape date.
2. Include any office or ambulatory BP values performed \geq 30 days post procedure date.
3. Use most recent remaining greater than 30 days post-procedure measurement up to 3 months, including unscheduled BP measurements.

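### The modified ITT and per-protocol sets drop subjects whose escape is first confirmed at the 3-month visit, so for this small group the endpoint value decides inclusion

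*SAP*

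**What the plan says.** - **Escape rule (Protocol 9.1.9).** It runs "from discharge up to and including the 3-month visit". After a first office SBP of 180 mmHg or more, "the subject will be seen a second time within 72 hours for a repeat office BP". Drugs restart if the value is still at or above 180. Restart for a safety concern is also allowed. Before drugs restart, "All efforts should be made to obtain an ABPM and Chem-7 panel".
- **Per-protocol set (SAP 7.1.3.3, item 4).** "Exclude Subjects meeting the anti hypertensive medication escape criteria". No timing is given, and nothing requires that drugs were restarted before the endpoint. Protocol 13.2.3 has the same exclusion, but with office SBP above 180 where the SAP has 180 or above.
- **Modified ITT set (SAP 7.1.3.2, Protocol 13.2.2).** The sentence opens "All enrolled subjects except subjects who meet the anti-hypertensive medication escape criteria" and ends "or safety reasons) will be excluded from the modified intention-to-treat population". Read literally it excludes everyone but the escapees; the evident intent is the reverse. It also sets no time limit.
- **ITT set (SAP 7.1.3.1).** Subjects "who meet the antihypertensive medication escape criteria (confirmed OSBP" at or above 180, or for safety reasons) stay in and "will be analyzed using Last Observation Carried Forward (LOCF) for their blood pressure measurements". Eligible values are those on or before the escape date and at least 30 days after the procedure, up to 3 months.
- **Rank (SAP 7.7.2.1).** ITT is primary; the other two sets are secondary.

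**The concern.** Escapees are normally left out of an off-drug analysis because restarted drugs contaminate the later endpoint. That reason does not apply to a subject whose escape is first confirmed at the 3-month visit. This subject has completed the off-drug period and has an uncontaminated 3-month office value. Change in office SBP at 3 months is itself an efficacy endpoint, so membership of the two secondary sets depends on the outcome being analysed. No passage exempts such a subject.

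The study asks whether the distal technique is as effective as the comparator procedure, with no margin and no powered hypothesis. Readers will look at the estimate and at whether it holds across the three sets. Removing poor responders overstates each cohort's own fall. If the cohorts truly differ, it also shrinks the difference between them.

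**Working it through.** **1. The plan's own figure.** The only efficacy figure behind the 50 subjects is the first-phase ambulatory change of -5.5 mmHg (95% CI -9.1 to -2.0, n = 38, p = 0.003). The half-width is (9.1 - 2.0)/2 = 3.55. Divided by t(37) = 2.026, this gives SE 1.752, hence t = -5.5/1.752 = -3.14 and p = 0.0033. It reproduces. There is no power calculation to check.

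**2. Who is affected.** Take a subject below 180 at the 2-week and 1-month office visits, then at or above 180 at 3 months and again within 72 hours. By 9.1.9 this is an escape. By SAP 7.1.3.3, and by the intent of 7.1.3.2, the subject leaves both secondary sets. By SAP 7.1.3.1 the 3-month office value, taken on or before the escape date, stays in ITT.

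**3. Inputs for size.**
- From the documents: baseline office SBP 150 to below 180; office difference 6.5 mmHg between denervation and sham (Protocol 3.1).
- SD of office change, from the first-80 interval -14.0 to -1.5 (Protocol 3.1): half-width 6.25 / t(78) 1.991 = SE 3.14; 3.14 / sqrt(1/38 + 1/42) = 14.0. The 42 is inferred as 80 - 38.
- Assumed, not in the documents: baseline mean 162, SD 7.5; mean change -9 in one cohort and -9 + 6.5 = -2.5 in the other; within-person SD w of 6 to 10; the 3-month response already present at 2 weeks and 1 month; the same filter in both cohorts.

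**4. Model.** A reading is B + d + e. B is the truncated baseline, d ~ N(mean change, 14² - w²) is fixed for the subject, and e ~ N(0, w²) is new at each reading. Escape at a visit needs two readings at or above 180. The outcome is the first 3-month reading minus B. The sets as written remove escapes at any of the three visits; the fix removes only those at 2 weeks or 1 month. Four million subjects were simulated per cohort.

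**5. Results.**

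| | w = 6 | w = 10 |
|---|---|---|
| First confirmed at 3 months (-9 cohort / -2.5 cohort) | 0.7% / 1.4% | 0.8% / 1.8% |
| Per 50 subjects, -2.5 cohort | 0.7 | 0.9 |
| Office difference, nobody removed | 6.5 | 6.5 |
| Sets as written | 5.4 | 5.7 |
| After the fix | 5.5 | 5.9 |
| Recovered by the fix (before rounding) | 0.15 | 0.25 |

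In the -9 cohort, removing the 3-month escapees exaggerates its own fall by about 0.2 mmHg. If only half the response is present at the earlier visits, the fix recovers 0.19 to 0.27 mmHg, so that assumption matters little.

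**6. Scale.** The unstratified 95% half-width for 50 against the 166 randomised to denervation is 1.96 × 14 × sqrt(1/50 + 1/166) = 4.4 mmHg.

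**The case against.** The strongest case against the point is that it hardly matters. ITT is primary and keeps the values. The study is unpowered. The modified ITT set is openly a set without escapees, reported beside ITT. The ABPM of a 3-month escapee is only to be sought, not guaranteed. The size rests on assumed inputs and compares raw mean changes, whereas the SAP stratifies by propensity score and adjusts for baseline by ANCOVA. All of this stands, and it limits the weight of the point. It does not supply a reason for removing an off-drug endpoint value because that value is high.

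Three stronger readings are tempting, and the documents do not support them.

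- **One reading at or above 180 is enough.** A reader might infer this because the two secondary definitions omit the word 'confirmed'. On that basis the 6.5 mmHg difference falls to 5.3, a loss of 18%. But the definitions refer to the escape criteria, and 9.1.9 and the titles of Protocol Tables 2 and 4 require a second set of measurements.
- **All the shrinkage comes from this rule.** Removing everyone confirmed at or above 180 at 3 months, and ignoring earlier visits, cuts 6.5 to between 5.7 and 6.0. That count includes subjects who would already have escaped at 2 weeks or 1 month and restarted drugs. The fix leaves them out, and they cause most of the loss.
- **The secondary sets always lean towards 'as effective'.** With equal cohorts and one rule for both, the between-study bias is nil. A true advantage of the distal technique would shrink as well. The lean arises only if the cohorts differ or only one is filtered. The SAP does not say how the HTN-OFF MED secondary sets are built, so the second case is open but not shown.

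**Conclusion.** The point holds for the two secondary efficacy sets and not for the primary ITT analysis. A subject whose escape is first confirmed at the 3-month visit is excluded on the endpoint value, although the office BP, and an ABPM if obtained before drugs restart, is off-drug.

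The effect is small: under one subject in 50, and about 0.15 to 0.25 mmHg of a 6.5 mmHg office difference, against a half-width of about 4.4 mmHg. This rests on the assumed baseline, mean changes and within-person SD, and on a 6.5 mmHg deficit that puts the distal technique no better than sham, an extreme case. It is worth correcting because the selection is avoidable and the correction needs only wording.

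**What to change.** In SAP 7.1.3.2 and 7.1.3.3, and Protocol 13.2.2 and 13.2.3:

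1. Exclude for escape only subjects with a confirmed escape, or a safety-reason escape, who restarted antihypertensive drugs before their 3-month off-drug measurements.
2. Keep subjects who first meet the criterion at the 3-month visit, with their observed off-drug values.
3. State that the same rule defines the HTN-OFF MED denervation sets.
4. Align the wording: add 'confirmed' as in the SAP ITT definition, correct the reversed modified ITT sentence, and reconcile above 180 (protocol per-protocol set) with 180 or above (SAP).

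Separately, Protocol 9.1.9 sends an escapee at the 3-month visit to the Table 4 schedule, while 9.1.10 takes any subject at 140 mmHg or more at that visit into medication re-introduction with a 4-month visit, which appears only in Table 3. These sections must be reconciled on follow-up; no clinical rule is proposed here.

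Cost: text changes in both documents, re-derivation of the HTN-OFF MED secondary sets, and slightly less favourable falls in the modified ITT and per-protocol results. No new data are needed.
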